9.4 Vital Sign Data

Vital signs include body temperature, heart rate, systolic blood pressure and diastolic blood pressure in supine and sitting position. In addition, body weight and waist circumference are measured. Potentially clinically relevant vital sign abnormalities will be listed by subject. Criteria for identifying vital signs of the potential clinical relevance are provided in [Appendix 2](#). Incidences of clinically relevant vital signs abnormalities based on the observation from the scheduled and unscheduled post-baseline visits will be tabulated safety samples. In addition to weight, BMI and waist circumference, vitals sign parameters at each trial week, and change from baseline at the post-baseline trial weeks will be summarized using descriptive statistics for the safety samples in the corresponding phases.

If vital sign assessments are repeated for the same trial week, the last repeat values will be used for production of mean change from baseline. This is accomplished by sorting patient data by visit date and visit time (if applicable) within the same visit identification.

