ⁱET procedures performed only on subjects not starting to meet stability at the open-label stabilization phase Week 8 visit and subjects not maintaining stability by the open-label stabilization phase Week 20 visit. These subjects will be discontinued from the trial.

^jVital signs include systolic and diastolic blood pressure and heart rate and will be performed at all in-clinic visits. Orthostatic assessments of blood pressure and heart rate will be made after the subject has been sitting for at least 5 minutes and again after the subject has been standing for approximately 2 minutes, but not more than 3 minutes. If a remote visit is converted to an in-clinic visit, vital signs will be recorded. Vital signs will not be collected for remote visits that are not converted to occur in-clinic.

^kA standard 12-lead ECG will be performed at rest after the subject has been lying down for approximately 5 minutes. ECGs will be evaluated at the investigational site to determine the subject's eligibility and to monitor safety. Based on the QTcF, a subject will be excluded if the correction is ≥ 450 msec (males) or ≥ 470 msec (females). Subjects with clinically significant ECG findings at screening may enter the open-label stabilization phase only after the screening ECG is repeated and determined by the investigator prior to treatment to have no abnormality(ies) that are clinically significant.

^lSubjects should fast for a minimum of 8 hours prior to blood draws for all laboratory assessments. If nonfasting blood samples are obtained initially for determining eligibility for the trial, a fasting blood sample should be drawn prior at or prior to the baseline visit (prior to the first dose of open-label drug). Subjects with clinically significant abnormal laboratory test results at screening may enter the open-label stabilization phase only after repeated laboratory test results are received and determined by the investigator prior to treatment to have no abnormality(ies) that are clinically significant.

^mIf the observed TSH level is outside of the normal range, tests of triiodothyronine (T3) and thyroxine (T4) levels will be assessed.

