3.7.3.3.2 Vital Signs

Vital sign measurements will include systolic and diastolic blood pressure and heart rate and will be performed at all in-clinic visits. If a remote visit is converted to an in-clinic visit, vital signs will be recorded. Vital signs will not be collected for remote visits that are not converted to occur in-clinic.

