7.1 Subject Disposition

Disposition of subjects including screened subjects and/or randomized subjects will be reported by phase and treatment group. Subject enrollment will be summarized by age group (6-12 years old and 13-17 years old), region, country and center. Durations of subjects staying in each phase will be summarized by treatment group. Reasons for discontinuations will be tabulated by phase and treatment group. Subjects who complete the Week 12 visit of the double-blind randomized withdrawal phase are defined as trial completers.

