7.2 Demographic and Baseline Characteristics

Demographic characteristics including age, weight, height, BMI, waist circumference, sex, race, ethnicity, region (North American, rest of world), categories for weight (< 50kg, >=50 kg) and age (7-12 years old and 12-17 years old) will be summarized using descriptive statistics (frequency, mean, median, standard deviation, maximum, minimum, and percentage when applicable) and reported by treatment group.

Disease characteristics at baseline and psychiatric history (including efficacy assessments and age of initial diagnosis for TD) will be presented by phase and treatment group. In

calculating age of first diagnosis for TD, if both month and day are missing, June 1 is used. If only day is missing, date of 1 is used. If only month is missing, month June is used.

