9.6.2 Suicidality

The incidence of suicidality, suicidal behavior and suicidal ideation will be calculated from the potential suicide events recorded on the C-SSRS (children's version) in the single-blind stabilization phase and double-blind randomized withdrawal phase for the safety samples. Suicidality will be assessed based on C-SSRS data. Data for the Baseline Version of the C-SSRS and Since Last Visit Version of the C-SSRS data will be summarized descriptively and presented in a listing.

The baseline version of C-SSRS is administered at the screening visit and the "Since Last Visit" version is administered at all subsequent visits. Baseline and post-baseline C-SSRS data will be summarized to report the incidence of suicidality, suicidal behavior and suicidal ideation. Suicidality is defined as reporting at least 1 occurrence of any suicidal behavior or suicidal ideation. Suicidal behavior is defined as reporting any type of suicidal behaviors. Suicidal ideation is defined as reporting any type of suicidal ideation.

In addition, C-SSRS data collected post-baseline will also be summarized to report the incidence of completed suicide, emergence of suicidal ideation, emergence of serious suicidal ideation, worsening of suicidal ideation and emergence of suicidal behavior. Any completed suicide is considered as complete suicidality. Emergence of suicidal ideation is defined as having no suicidal ideation at screening and baseline and reporting any type of ideation during treatment. Emergence of serious suicidal ideation is defined as having no suicidal ideation at screening and baseline and reporting any type of suicidal ideation with ideation severity rating of 4 or 5 during treatment. Worsening of suicidal ideation is defined as occurring when the most severe suicidal ideation rating during treatment is more severe than its worst rating at screening and baseline. Emergence of suicidal behavior is defined as having no suicidal behavior at screening and baseline and reporting any type of suicidal behavior during treatment.

10 Pharmacokinetic Analyses

None.

11 Pharmacodynamic Analyses

None.

12 Pharmacogenomic Analyses.

None.

13 Interim Analysis

None.

14 Changes in the Planned Analyses

This trial was terminated due to withdrawal of postmarketing commitment, so the interim analysis specified in the protocol was not to be conducted. The descriptive statistics will be provided for all the efficacy endpoints.

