Appendix 2 Criteria for Identifying Vital Signs of Potential Clinical Relevance

Variable	Criterion Value^a	Change Relative to Baseline^a
Heart Rate ^b	> 120 bpm < 50 bpm	≥ 15 bpm increase ≥ 15 bpm decrease
Systolic Blood Pressure ^b	> 180 mmHg < 90 mmHg	≥ 20 mmHg increase ≥ 20 mmHg decrease
Diastolic Blood Pressure ^b	> 105 mmHg < 50 mmHg	≥ 15 mmHg increase ≥ 15 mmHg decrease
Weight	-	≥ 7% increase ≥ 7% decrease

^a In order to be identified as potentially clinically relevant, an on-treatment value must meet the “Criterion Value” and also represent a change from the subject’s baseline value of at least the magnitude shown in the “Change Relative to Baseline” column.

^b As defined in “Supplementary Suggestions for Preparing an Integrated Summary of Safety Information in an Original NDA Submission and for Organizing Information in Periodic Safety Updates,” FDA Division of Neuropharmacological Drug Products draft (2/27/87).

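### Three SAP reporting rules are wrong as written: vital-sign positions (9.4), demographic age bands (7.2) and the mapping of pre-dose Day 1 ratings to open-label Week 1 (3.4 with 9.6.1)

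*SAP*

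**What the plan says.** **Vital signs.** SAP 9.4: "Vital signs include body temperature, heart rate, systolic blood pressure and diastolic blood pressure in supine and sitting position". It plans descriptive change from baseline by trial week and incidence of clinically relevant values, and adds a repeat rule: "If vital sign assessments are repeated for the same trial week, the last repeat values will be used". Protocol 3.7.3.3.2 has a shorter list: "Vital sign measurements will include systolic and diastolic blood pressure and heart rate and will be performed at all in-clinic visits". Footnote j of protocol Table 3.7-1 (open-label) and footnote c of Table 3.7-2 (double-blind) set the positions: readings are taken "after the subject has been sitting for at least 5 minutes and again after the subject has been standing for approximately 2 minutes".

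**Age.** Protocol 3.4.2 admits ages 6 to 17 inclusive, and SAP 3.1 and 3.3.1 repeat that range. For enrolment, SAP 7.1 uses "age group (6-12 years old and 13-17 years old". For demographics, SAP 7.2 uses "age (7-12 years old and 12-17 years old".

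**Windows.** SAP 3.4 derives Trial Day from dates alone, so the date of first dose is Day 1. Table 3.4-1 sets Week 1 at Days 1 to 10 in both phases and has no baseline row. The last observation in a window is used, and the mapping covers everything reported by trial week. SAP 9.6.1 reports change in the extrapyramidal (EPS) scales (SAS, BARS and AIMS) by trial week.

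**Context.** SAP 14: "This trial was terminated due to withdrawal of postmarketing commitment, so the interim analysis specified in the protocol was not to be conducted". Efficacy is reported descriptively, and SAP 8.1.1 provides only the relapse rate for the primary endpoint.

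**The concern.** After early termination the report is descriptive, so a wrong reporting rule goes straight into a table with no inferential analysis beside it. Safety and tolerability are the trial's secondary objective.

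- **Vital signs.** The protocol calls the paired readings orthostatic assessments, so the standing value is the reason for the second reading. SAP 9.4 does not mention it, and names a position and a measurement that the protocol does not schedule. At stake are the mean-change tables CT-11.1.1 and CT-17.1.1.
- **Age.** The demographic bands are neither exhaustive nor exclusive over the eligible range, and the SAP disagrees with itself. At stake is whether CT-3.1.1 and CT-3.1.2 agree with CT-1.3.1 and CT-1.3.2.
- **Windows.** A rating taken before any drug can be labelled as Week 1 of treatment. At stake is a spurious row in CT-13.1.1 to CT-13.1.3.

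**Working it through.** The plan states no figure to reproduce here. The check sets the rules against the schedule and counts.

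**(a) Vital signs**

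- Protocol: 3 measures (systolic, diastolic, heart rate) × 2 positions (sitting, standing) = 6 scheduled parameters. No temperature or supine reading is scheduled; lying down is specified only for the ECG.
- SAP 9.4, if position applies to heart rate as well as pressure: temperature + 3 measures × 2 positions (supine, sitting) = 7. The overlap is the 3 sitting measures, so 7 − 3 = 4 named parameters have no scheduled data and 6 − 3 = 3 scheduled parameters are not named.
- SAP 9.4, if position applies to pressure only: temperature + heart rate + 2 pressures × 2 positions = 6. Three have no scheduled data (temperature and two supine pressures). Of the 4 pressure readings collected, the 2 standing ones are not named.

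**(b) Age bands**

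| Age | SAP 7.2 bands containing it | SAP 7.1 bands containing it |
|---|---|---|
| 6 | 0 | 1 |
| 7 to 11 | 1 | 1 |
| 12 | 2 | 1 |
| 13 to 17 | 1 | 1 |

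Two of the 12 eligible single-year ages fail: age 6 is unassigned and age 12 is assigned twice. Write n6 and n12 for the numbers of subjects of those ages. In one and the same sample:

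- count in 7-12 = count in 6-12 − n6
- count in 12-17 = count in 13-17 + n12
- sum of the two SAP 7.2 bands = N − n6 + n12, which equals N only if n6 = n12

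CT-1.3.2 and CT-3.1.2 both name the Randomized Sample, so the comparison is direct there. CT-1.3.1 names no sample, so its comparison with CT-3.1.1 assumes the two share one. The documents do not give n6 or n12.

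**(c) Open-label Week 1**

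1. Protocol 3.7.1.2 puts SAS, BARS and AIMS among the procedures completed before dosing, and gives the first dose at the same clinic visit. Hence Trial Day = 0 + 1 = 1, which falls in Week 1 (Days 1 to 10). Screening ratings (Days −42 to −3) fall in no window.
2. The next scheduled open-label EPS rating is Week 8, Day 57 ± 3 = Days 54 to 60, in the Week 8 window. The earliest is 54 − 10 = 44 days after the Week 1 window closes.
3. The end-of-phase rating comes at Week 14, 16, 18 or 20 (Days 96–102, 110–116, 124–130 or 138–144), each inside its own window.
4. No scheduled rating displaces the Day 1 record under the last-observation rule; only an early-termination or unscheduled rating by Day 10 would. The mapped change is baseline minus itself, which is 0.
5. SAP 9.4 limits change from baseline to post-baseline weeks, and SAP 9.3 and 9.5 refer to scheduled weeks. SAP 9.6.1 has neither limit.

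Elsewhere the schedule largely protects the tables. YGTSS and CGI-TS Severity are rated at open-label Week 1, so the later value displaces the Day 1 record in subjects who attend. In the double-blind phase, EPS is rated at Week 1 (Days 6 to 10), with the same effect.

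**The case against.** - **These are slips that a programmer would catch.** This is partly right. SAP 7.1 gives workable bands one section earlier, and overlapping bands would surface at once. SAP 5.2 already defines the pre-dose visit as open-label baseline, and protocol 7.6.5.1 presents EPS results by visit. A zero row would be easy to recognize and would leave the Week 8 and end-of-phase results unchanged. So the consequences in (b) and (c) are possible, not certain. The written rules still need correcting, because the SAP is what gets programmed.
- **The repeat rule.** A reader might infer that it discards one of the two positions. The text does not support that: sitting and standing readings are two scheduled measurements under different conditions, not repeats of one.
- **The incidence tables.** A reader might infer that standing values are excluded from CT-11.2 and CT-17.2. Appendix 2 begins "In order to be identified as potentially clinically relevant, an on-treatment value must meet the" criterion, with no position limit, and SAP 9.4 counts scheduled and unscheduled post-baseline observations. The natural reading is that any collected value counts.
- **An undeclared change.** SAP 14 is silent on vital signs, but nothing shows a deliberate change of plan. A wording error fits equally well.
- **Adverse events.** Protocol 7.6.1.1 and 7.6.1.2 already confine the summaries to events during each phase, so the loose first limb of the TEAE definition in SAP 9.2 is a wording point only.

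**Conclusion.** The point stands for three rules, with limited reach.

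- **SAP 9.4.** The position label and temperature do not match the protocol. Three of 6 scheduled parameters lack a planned mean-change summary (or 2 of 4 pressure readings if position applies to pressure only), and 4 of 7 (or 3 of 6) named parameters have no scheduled data.
- **SAP 7.2.** Two of 12 eligible ages fail, one unassigned and one double-assigned. The effect on counts is n6 and n12, which depend on actual enrolment.
- **SAP 3.4 with 9.6.1.** Three open-label tables could gain a Week 1 row of zero change, assuming that the rules are programmed literally and that ratings and first dose share a date, as protocol 3.7.1.2 provides.

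As scheduled, the effects fall on descriptive safety and demographic tables. The documents give no ground for inferring that the relapse rate or any efficacy conclusion is at risk.

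There are two smaller wording faults. SAP 9.2 refers to an intramuscular depot that is not among the trial treatments, and does not tie its first TEAE limb to a phase. SAP 3.1.2 and protocol 3.1 contradict each other on whether an excursion is allowed at the randomization visit.

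**What to change.** 1. **SAP 9.4:** replace supine and sitting with sitting and standing, delete body temperature, and summarize change from baseline by position. One clause can confirm that both positions count under Appendix 2.
2. **SAP 7.2:** use the SAP 7.1 bands, 6-12 and 13-17 years. Each eligible age then falls in exactly one band.
3. **SAP 3.4:** keep Days 1 to 10. State that, when records are mapped to the weeks of a given phase, those taken before that phase's first dose are its baseline and are not assigned to its post-baseline weeks. Add that this does not alter their mapping within the earlier phase. Without that limit the rule would strip open-label records, since all of them precede the first double-blind dose; with it, end-of-phase ratings remain open-label Week 14 to 20 data. Starting Week 1 at Day 2 would also remove the zero row, but would drop any genuine post-dose Day 1 record.
4. **Minor:** in SAP 9.2, delete the depot reference and tie the first TEAE limb to the first dose of the relevant phase. Reconcile SAP 3.1.2 with protocol 3.1 on excursions at the randomization visit.

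The cost is a few words in the SAP and minor programming, with no new data.

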2.1 Trial Rationale

The goal of this trial is to evaluate the longer-term efficacy of aripiprazole in pediatric subjects (6 - 17 years) for the treatment of TD. The trial has a pretreatment phase, up to a 20-week open-label stabilization phase, a 12-week double-blind randomized withdrawal

Protocol 31-14-204

phase, and a 1 month follow-up period after the last dose of IMP or after the clinical site is notified that the subject discontinued the IMP. The proposed age range for the population in this trial is 6 to 17 years, inclusive. These age ranges are based on published data indicating that tics associated with TD show the greatest severity at 10 years of age. Previous TD trials demonstrated the efficacy of aripiprazole over an 8-week period. This trial is part of the US Food and Drug Administration (FDA) post-marketing commitment to evaluate the longer-term efficacy of aripiprazole.

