9.	The subject represents a significant risk of committing suicide based on history (suicide attempt in past 1 year), routine psychiatric status examination, investigator's judgment, or who have an answer of "yes" on any question other than 1-3 (current or over the last 30 days) on the baseline/screening version of the C-SSRS.
10.	The subject has a body weight < 16 kg.
11.	Subjects who have taken neuroleptic or antiparkinson drugs within 14 days prior to baseline.
12.	Subjects requiring CBT for TD during the trial period. CBT for other nonexclusionary disorders must remain consistent throughout the trial.
13.	The subject has met DSM-5 criteria for any significant psychoactive substance use disorder within the past 3 months.
14.	A positive drug screen for cocaine, alcohol, or other drugs of abuse (excluding caffeine, nicotine, or prescribed psychostimulants for ADHD). Investigators can choose to repeat a positive drug screen one time during screening period after concurrence from the medical monitor. A second positive test for any drug of abuse would be exclusionary.
15.	Subject requiring medication not allowed per protocol.
16.	Use of any CYP2D6 and CYP3A4 inhibitors or CYP3A4 inducers within 14 days prior to baseline and for the duration of the trial.
17.	Other nutritional or dietary supplements and nonprescription herbal preparations for TD (eg, cannabinoids, N-acetylcysteine, omega-3 fatty acids, kava extracts, GABA supplements) within 7 days prior to baseline and for the duration of the trial, unless approved in advance by the medical monitor.
18.	The inability to swallow tablets or tolerate oral medication.
19.	Subject has participated in a clinical trial involving either study medication or interventional (non-medication) treatment for TD within the last 60 days.
20.	The following laboratory test results, vital signs and ECG results are exclusionary: 
 a) Platelets $\leq 75,000/\text{mm}^3$ b) Hemoglobin ≤ 9 g/dL c) Neutrophils, absolute $\leq 1000/\text{mm}^3$ d) AST $> 3 \times \text{ULN}$ as defined by the central laboratory e) ALT $> 3 \times \text{ULN}$ as defined by the central laboratory f) Creatinine ≥ 2 mg/dL g) Diastolic blood pressure > 105 mmHg h) QTc ≥ 450 msec (males) or ≥ 470 msec (females) using the QTcF correction.

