7.6.3 Physical Examination, Vital Signs, Body Weight, and Waist Circumference Data

The incidence of potentially clinically relevant vital sign abnormalities and body weight change will be reported for the open-label stabilization phase and by treatment group for the double-blind randomized withdrawal phase with the safety samples appropriate to each phase. Vital sign parameters, body weight, and waist circumference will also be evaluated by their changes from trial baseline for the Open-label Safety Sample and by change from randomization baseline for each treatment group for the Randomized Safety Sample. The BMI values will be calculated based on height and weight measurements and its results will be summarized by change from baseline similarly to body weight. Physical examination data will be listed.

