3.1 Type of Trial

This phase 3b/4 trial is a randomized, double-blind, placebo-controlled trial to evaluate the long-term efficacy of oral aripiprazole in the treatment of pediatric subjects with TD. Subjects, 6 to 17 years of age, are recruited at approximately 70 sites globally. The trial consists of 3 distinct phases: a pretreatment phase, an open-label stabilization phase, and a double-blind randomized withdrawal phase. Screening assessments may occur during 1 or more visits (as needed) and must occur in the clinic. The baseline visit occurs in the clinic, as well the open-label stabilization phase visits on Weeks 1, 2, 4, 8, 12, 14, 16, 18, and 20 and the double-blind, randomized withdrawal phase visits at Weeks 1, 2, 4, 8, and 12. All other visits occur via telephone, web, in-clinic, or other acceptable means of contact. The trial schematic is presented in [Figure 3.1-1](#).

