3.2.1 Open label Stabilization Phase

All enrolled subjects begin treatment at a 2.0 mg/day dose, with the dose titrated to 5.0 mg/day after 2 days. Subsequent dose adjustments in set increments are based on the subject's weight at baseline to achieve optimum control of tics up to the maximum recommended doses based on the US labeling, presented in [Table 3.2.1-1](#).

Weight Group	Dosing Adjustments	Target Doses for Stabilization	Maximum Dose
< 50 kg	5 mg and 10 mg	5 mg and 10 mg	10 mg/day
≥ 50 kg	5 mg, 10 mg, and 20 mg	10 mg and 20 mg	20 mg/day

All enrolled dose titration schedule per weight group is provided in [Table 3.2.1-2](#). Subjects with body weight < 50 kg must remain on a minimum stable dose of 5.0 mg or maximum 10.0 mg for a minimum of 12 weeks. Subjects with body weight ≥ 50 kg must achieve a dose of 10.0 mg no later than Week 4 and remain on a stable dose of 10.0 mg or 20.0 mg for a minimum of 12 weeks. For the remainder of the 12-week period, subjects can remain of 10.0 mg or titrate to 20.0 mg as long as efficacy is stable. In order to be titrated from 10.0 mg to 20.0 mg, subject must remain on a dose of 15.0 mg for 1 week (i.e., at least 4 days) prior to being titrated to 20.0 mg. If a subject is titrated to 20.0 mg and subsequently requires down-titration, their dose is reduced to 10.0 mg. If the dose is up-titrated again, the dose must increase from 10.0 mg to 20.0 mg without a 15.0 mg step. Subjects are allowed 1 down titration (only to the minimum dose to achieve stabilization) and a return to the prior maximum dose during the open-label stabilization phase. Up-titration can only occur at scheduled visits, but down-titration may occur at either scheduled or unscheduled visits. Dose adjustments, and a subsequent return to the higher dose, are not allowed after the Week 8 visit. If a subject experience an AE or tolerability issues after the Week 8 visit that require the dose to be down-titrated, regardless of dose level, they must be discontinued. Subjects who meet the YGTSS TTS criteria for stability and remain on a stable dose of IMP for 12 weeks may be randomized into the double-blind phase of the trial prior to the Week 20/EOP visit.

Body Weight	Day 1 (Baseline)	Week 1	Week 2	Week 4	Week 8^a	Weeks 12 to 20^a
< 50 kg	2.0 mg starting dose, increased to 5.0 mg after 2 days	5.0 mg or increase to 10.0 mg	5.0 mg or increase to 10.0 mg	5.0 mg or increase to 10.0 mg	5.0 mg or increase to 10.0 mg	5.0 mg or 10.0 mg

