- CT-16.1.4 Laboratory Test Results for Other Clinical Laboratory Tests - Mean Change from Baseline (Open-Label Safety Sample)
- CT-16.2 Incidence of Laboratory Values of Potential Clinical Relevance (Open-Label Safety Sample)
- CT-17.1.1 Vital Sign Parameters - Mean Change from Baseline (Open-Label Safety Sample)
- CT-17.1.2 Mean Change from Baseline in Weight, Height, BMI and Waist Circumference (Open-Label Safety Sample)
- CT-17.2 Incidence of Vital Signs of Potential Clinical Relevance (Open-Label Safety Sample)
- CT-18.1 ECG Parameters - Mean Change from Baseline (Open-Label Safety Sample)
- CT-18.2 Incidence of ECG Measurements of Potential Clinical Relevance (Open-Label Safety Sample)

- DREAS-1 Discontinued Subjects and Reasons for Discontinuation
- DREAS-2 Adverse Events for Subjects Who Discontinued from Trial due to Withdrew Consent
- PDEV-1 Protocol Deviations by Phase and Type of Deviation (Enrolled Sample)
- PDEV-2 Protocol Deviations by Phase, Country, Center and Type of Deviation (Enrolled Sample)
- PDEV-3 All Protocol Deviations by Subject
- PDEV-4 Protocol Deviations Criteria
- DEMOG-1 Demographic Characteristics
- SMED-1.1 Summary of Trial Medication Compliance in Double-Blind Randomized Withdrawal Phase (Randomized Sample)
- SMED-1.2 Trial Medication Compliance in Double-Blind Randomized Withdrawal Phase (Randomized Sample)
- SMED-2.1 Summary of Trial Medication Compliance in Open-Label Stabilization Phase (Enrolled Sample)
- SMED-2.2 Trial Medication Compliance in Open-Label Stabilization Phase (Enrolled Sample)

Protocol 31-14-204

EFF-1 Relapse Data

EFF-2.1 Yale Global Tic Severity Scale - Total Tic Score (YGTSS - TTS) and Total Yale Global Tic Severity Scale Score

EFF-2.2 Clinical Global Impressions Scale for Tourette's Syndrome (CGI-TS) Severity and Improvement Scores

AE-1.1 Adverse Events in Open-Label Stabilization Phase (Enrolled Sample)

AE-1.2 Adverse Events in Double-Blind Randomized Withdrawal Phase (Randomized Sample)

AE-1.3 Adverse Events in Follow-up Period (Enrolled Sample)

LAB-1 Laboratory Test Results: Serum Chemistry

LAB-2 Laboratory Test Results: Hematology

LAB-3 Laboratory Test Results: Urinalysis

LAB-4 Laboratory Test Results: Other Laboratory Tests

LAB-5 Laboratory Test Results: Urine Drug Screen

LAB-6 Laboratory Test Results: Urine Pregnancy Test (Enrolled Sample)

Proposed Patient Data Listings

PDATA-1 Consents and Eligibility

PDATA-2 Randomization List

PDATA-3.1 Subject Disposition

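### Open-label weight and BMI change in 6- to 17-year-olds is reported without any growth-standardised measure, so CT-17.1.2 and CT-17.2 mix expected growth with drug-related change

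*SAP*

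**What the plan says.** Weight, BMI and waist circumference are listed safety endpoints (Protocol 3.5.2, SAP 6.4), and safety and tolerability is the secondary objective.

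- **Change from baseline.** SAP 9.4 plans descriptive statistics by trial week: "In addition to weight, BMI and waist circumference, vitals sign parameters at each trial week, and change from baseline". Protocol 7.6.3 handles BMI like weight: "its results will be summarized by change from baseline similarly to body weight". The open-label table is CT-17.1.2, "Mean Change from Baseline in Weight, Height, BMI and Waist Circumference (Open-Label Safety Sample").
- **Flag.** SAP Appendix 2 (and Protocol Appendix 1) sets "≥ 7% increase ≥ 7% decrease" for weight. Heart rate and blood pressure must meet both an absolute value and a change; weight has no absolute value, so percent change alone triggers the flag. BMI and waist circumference have no flag. CT-17.2 gives the open-label incidence. Under SAP 9.4 the incidence draws on all scheduled and unscheduled post-baseline visits.
- **Population.** "Subjects, 6 to 17 years of age, are recruited at approximately 70 sites globally" (SAP 3.1). The lower weight limit is an exclusion: "The subject has a body weight < 16 kg" (Protocol 3.4.3).
- **Duration and control.** Protocol 2.1 describes up to a "20-week open-label stabilization phase". It has no comparator: "All enrolled subjects begin treatment at a 2.0 mg/day dose, with the dose titrated to 5.0 mg/day after 2 days" (SAP 3.2.1).

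Neither document mentions a z-score, percentile, growth reference or other age- and sex-standardised measure for weight, height or BMI.

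**The concern.** Weight and height normally rise over several months in this age range, and BMI changes with age. A raw change in kg or kg/m², or a fixed percentage of baseline weight, therefore includes growth. With no control group in the open-label phase, nothing in CT-17.1.2 or CT-17.2 separates growth from a drug effect.

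The growth component also differs between subjects. It depends on age and size, and on time on study: a subject may leave at Week 8 for lack of response, be randomised from Week 14, or stay to Week 20. CT-17.2 pools all of these, and no safety table in SAP Appendix 4 is split by age.

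Weight gain is a relevant signal for this drug. In the 52-week open-label extension described in Protocol 1.2.2, 5 of the 10 subjects whose adverse events led to discontinuation stopped for increased weight. What is at stake is how the open-label safety tables are read. The primary endpoint is not affected.

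**Working it through.** The plan gives no figure to reproduce, so this is an illustration of size.

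**Inputs from the documents:** ages 6 to 17; open-label phase up to 20 weeks, randomisation from Week 14, non-responders discontinued at Week 8; flag at 7% of baseline weight; minimum weight 16 kg.

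**Assumption, not in the documents:** normal growth of 2 to 5 kg a year, paired with body weight as in the table.

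**Step 1. Growth as a percentage of baseline weight.** Growth % = annual gain (kg) × weeks/52 ÷ weight (kg) × 100. For example, 5 × 20/52 ÷ 40 = 4.8%.

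| Assumed child | Week 8 | Week 14 | Week 20 | Week 20 as share of 7% |
|---|---|---|---|---|
| 25 kg, 2.5 kg/year (same result for 20 kg at 2 and 30 kg at 3) | 1.5% | 2.7% | 3.8% | 55% |
| 40 kg, 5 kg/year | 1.9% | 3.4% | 4.8% | 69% |
| 60 kg, 3 kg/year | 0.8% | 1.3% | 1.9% | 27% |

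**Step 2. What the flag then measures at Week 20.** The gain beyond growth needed to trigger the increase flag is 7 − 4.8 = 2.2% in the 40 kg child and 7 − 1.9 = 5.1% in the 60 kg child. For the decrease flag, growth works the other way: the loss relative to expected weight must be about 7 + 1.9 = 8.9% to 7 + 4.8 = 11.8%.

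**Step 3. Growth needed to reach 7% unaided by Week 20.** Annual gain = 0.07 × weight ÷ (140/365.25). This is 2.9 kg/year at 16 kg, 5.5 kg/year at 30 kg and 9.1 kg/year at 50 kg.

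**Step 4. Possible effect on flag incidence.** This needs further assumptions: growth of 5% to 15% of body weight a year, and normally distributed 20-week change with a stated SD. Mean change m = annual % × 140/365.25, which gives 1.9% to 5.8%. P(flag) = 1 − Φ((7 − m)/SD).

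| SD (percentage points) | No growth | 5%/year | 10%/year | 15%/year |
|---|---|---|---|---|
| 2 | 0.02% | 0.6% | 5.7% | 26.6% |
| 3 | 1.0% | 4.5% | 14.6% | 33.8% |
| 4 | 4.0% | 10.2% | 21.4% | 37.7% |

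The direction is the same throughout. The size depends heavily on assumptions the documents do not settle.

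**Step 5. How far BMI helps.** Assuming height growth of 6 to 8 cm a year at 120 to 155 cm, height squared rises by 3.3% to 4.0% over 20 weeks. That is similar in size to the weight growth in the lighter children above, so BMI removes a good part of it. It does not remove the change of BMI with age. In addition, Protocol 3.7.3.3.3 allows BMI to use the closest preceding height. Height is scheduled at baseline and Weeks 8, 16 and 20, and weight also at Weeks 4 and 12. At those two visits the height is four weeks old, which overstates BMI by about 0.7% to 0.8% under the same assumption.

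**The case against.** The strongest reply is that the package already offers other routes. CT-17.1.2 shows height, BMI and waist circumference beside weight. Flagged values are listed by subject (CT-11.3.1). Adverse events judged drug-related, or leading to discontinuation, are tabulated for the open-label sample (CT-15.3.1, CT-15.6.1). The 7% row is a screen for potential clinical relevance, not an attribution measure. After early termination the SAP is descriptive, and z-scores could be derived later. All of this is fair and limits the consequence. None of it takes growth out of the two tables, and a measure specified in advance is preferable to one added after the results are seen.

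Four stronger readings are tempting, and the documents do not support them.

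- A reader might infer that growth distorts the double-blind comparison too, through age imbalance in small arms. The concurrent placebo arm is expected to grow similarly, and randomisation is stratified by baseline weight below or at least 50 kg (Protocol 3.6.1). Growth stays in the within-arm changes but largely cancels between arms.
- A reader might take the 7% flag to cover BMI. It applies to weight only.
- A reader might conclude that growth alone commonly triggers the flag. None of the three profiles in Step 1 reaches 7%, 20 weeks is the upper bound, and the incidences in Step 4 rest on an assumed SD.
- A reader might call weight the leading tolerability signal. The 5 of 10 discontinuations are documented, but the 45 subjects with related events in Protocol 1.2.2 pool weight increase, somnolence and fatigue. The common reactions in Protocol 1.3 name increased appetite, not weight increase.

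**Conclusion.** The point holds for the uncontrolled open-label tables. CT-17.1.2 and CT-17.2 mix expected growth with drug-related change, by an amount that varies with age and time on study, and no age- and sex-standardised measure is planned. Under the assumed 2 to 5 kg a year, growth alone accounts for 27% to 69% of the 7% threshold at the 20-week maximum, and less for subjects who leave or are randomised earlier. Those figures are illustrative, because they depend on growth rates outside the documents and on the pairing of rate with weight. The qualitative conclusion needs only that children of these ages grow. The effect is on the interpretation of a secondary safety objective, and the improvement is worthwhile because it is cheap.

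**What to change.** - In SAP 9.4 and CT-17.1.2, add change from baseline in age- and sex-standardised weight, height and BMI z-scores. Use one growth reference named by the sponsor and exact age at each visit. Add the same rows to CT-11.1.2 for consistency.
- Optionally, add to CT-17.2 a category for increase in BMI z-score. The sponsor must justify and pre-state the cut-off, since the documents give no basis for one.
- Keep the raw-change and 7% rows, with a footnote that they are unadjusted for growth.

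The cost is SAP wording, some programming and a few table rows. Age, sex, height and weight are already collected, so no visit or procedure changes. There are two limits: a single reference is applied across all regions, and z-scores remove average growth but do not replace a control group.
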